13.2.2 Primary endpoint

There are two planned analyses of the primary endpoint variable: an interim analysis at N1 = 21 patients per group and a final analysis at N = 70 patients per group. Two sample *t*- statistics will be calculated and evaluated as described in 13.2.1.

Multiple imputation will be used to replace missing end of treatment values of the National Institutes of Health-Chronic Prostatitis Symptom Index (NIH-CPSI) total score. A sensitivity analysis will replace missing values by the largest (i.e. worst) observed value.

In addition to formal testing for a difference between groups, the mean change between groups and the mean change within each group together will be reported together with 95% confidence intervals.

Version Date: 11APR2023

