11.5 Questionnaire administration

All questionnaires will be completed in the clinic by the patient prior to starting study therapy and after completing six weeks of daily Q-Urol/Placebo therapy.

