12.3.2 Evaluable for response

A modified intent-to-treat data set will be used to assess efficacy. Subjects who have successfully undergone brachytherapy and received one dose of Q-Urol will be evaluable for response. Subjects who fail to undergo brachytherapy or begin Q-Urol therapy will be replaced. Those who do not complete the end of treatment patient questionnaires will be considered treatment failures.

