13.2 Statistical Analyses

13.2.1 Sample size determination

The outcome for sample size determination is the primary endpoint variable, the peak of the National Institutes of Health-Chronic Prostatitis Symptom Index (NIH-CPSI) total score measured from baseline to six weeks post brachytherapy. The primary hypothesis is that the mean of the primary outcome variable will be $\frac{1}{2}$ standard deviation lower in patients taking Q-Urol compared to placebo. A single interim analysis is planned after N1= 21 subjects per group have outcome data. The interim and final analysis will compare the treatment and control means using nominal t statistics (control minus treatment). If the t statistic has a value less than -1.16 at the interim analysis the trial will be terminated for futility. If the t statistic has a value greater than 2.85 at the interim analysis the trial will be terminated for efficacy.

If the study is not terminated for efficacy or futility at the interim analysis an additional N2 = 49 patients per group will be accrued for a total of N = 70 patients per group. If the interim analysis is done at the planned sample size (21 patients per group) the treatment will be deemed efficacious at the final analysis if the t statistic has a nominal value greater than 1.67.

The above design was evaluated using 100,000 simulated data sets for both the null and alternative hypotheses. There is 90% power at overall one-sided Type I error equal to 0.05 (one-sided) to detect a 0.5 standard deviation lower mean of the primary endpoint in the treatment group compared to the control group. The probability of early termination for futility under the null hypothesis is 12%. The probability of early termination for futility under the alternative hypothesis is 0.3%. The probability of early termination for efficacy under the alternative hypothesis is 12%.

If the interim analysis or final analysis is performed at a sample size that is different than the planned sample size the final analysis will be adjusted to maintain an overall Type I error of no more than 0.05 (one-sided).

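### The only missing-data sensitivity analysis for the primary endpoint is not reliably conservative: its direction depends on which arm loses more patients

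*Combined protocol and SAP*

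**What the plan says.** Section 13.2.2 sets the main method: "Multiple imputation will be used to replace missing end of treatment values" of the NIH-CPSI total. It gives no imputation model and no number of imputations. It then names a single sensitivity analysis: "A sensitivity analysis will replace missing values by the largest (i.e. worst) observed value". The text does not distinguish the arms and does not say whether the maximum is taken over all patients or within each arm. One maximum over all patients is the plain reading.

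Section 12.3.2 has a separate rule for the same patients: "Those who do not complete the end of treatment patient questionnaires will be considered treatment failures". Failure is not defined for an endpoint that is a mean score, and the rule is not linked to either method in Section 13.2.2.

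Section 11.5 fixes the time points: "All questionnaires will be completed in the clinic by the patient prior to starting study therapy", and again after six weeks. Under Section 13.2.1 the t statistic is control minus treatment, so a higher placebo mean favours Q-Urol. No expected dropout rate appears anywhere.

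**The concern.** Multiple imputation as usually run assumes data are missing at random, and observed data cannot confirm that. A sensitivity analysis should therefore show how far the conclusion survives if the unseen patients differ from the seen ones.

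Informative loss is foreseeable. Sections 7.4.1, 7.4.2 and 8.1 allow patients to leave for toxicity, non-compliance, intercurrent illness or request. The form is completed in clinic, near the symptom peak that Section 2.1 describes.

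Filling both arms with one extreme score does not ask the useful question, which is how much worse the unseen Q-Urol patients would have to be to overturn a positive result. Agreement with multiple imputation could simply reflect more placebo loss, and disagreement could simply reflect dilution. At stake is whether the one planned robustness check can be interpreted, not the primary decision rule.

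**Working it through.** **Inputs from the documents.** Section 13.2.1 gives 70 per arm, a final cut-off of t > 1.67, an interim look at 21 per arm with bounds -1.16 and 2.85, a 0.5 SD target, one-sided 0.05 and 90% power. The score range from Appendix 1 is 4 + 2 + 5 + 10 + 5 + 5 + 3 + 3 + 6 = 43, so 0 to 43.

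**Assumptions not in the documents.** Scores are roughly normal with mean 18 and SD 8, rounded and clipped to 0-43. Losses are completely at random in fixed numbers, with 5%, 10% and 15% of 70 taken as 4, 7 and 10 patients. There is no interim look in the missing-data runs. Intermediate quantities in steps 2 and 3 come from a parallel run with placebo mean 20 and SD 8, whose pass rates agree closely.

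**Step 1: the plan's own figures.** Simulating the two-stage t-test gives Type I error 0.050, power 0.900, futility stopping 12.5% (null) and 0.3% (alternative), and efficacy stopping 12.5% (alternative). The plan states 0.05, 90%, 12%, 0.3% and 12%, so the design reproduces.

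**Step 2: the shift.** Let p_C and p_T be the missing fractions and M the filled value. The expected filled difference is

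D = (1 - p_C)μ_C + p_C·M - (1 - p_T)μ_T - p_T·M.

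- No effect: D = (p_C - p_T)(M - μ). With 10 placebo and 4 Q-Urol patients lost, simulated D is 0.217 SD, so M sits 0.217 / (6/70) = 2.53 SD above the mean. With 7 and 4 lost, D = (3/70) × 2.53 = 0.108 SD.
- Equal loss: D = (1 - p)(μ_C - μ_T). At 10%, 0.9 × 0.494 = 0.444 SD (0.494 rather than 0.5 because of clipping).

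**Step 3: the pass rate by hand.** √(2/70) = 0.169. Filled values are constants, so only the observed scores vary, while the t-test treats all 140 as data. At 15%/5% and at 10%/10%, 126 scores are observed, and the true standard error is 0.99 × √126 / 70 = 0.159 SD (0.99 is the SD ratio after clipping).

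- No effect, 15%/5%: the SD is inflated 1.207-fold, so the nominal standard error is 1.207 × 0.169 = 0.204. Mean t = 0.217 / 0.204 = 1.06; SD of t = 0.159 / 0.204 = 0.78. P(t > 1.67) = 1 - Φ((1.67 - 1.06) / 0.78) = 0.22.
- No effect, 10%/10%: nominal standard error 1.212 × 0.169 = 0.205; SD of t = 0.775. P = 1 - Φ(1.67 / 0.775) = 0.016.
- True 0.5 SD, 10%/10%: nominal standard error 1.229 × 0.169 = 0.208; mean t = 0.444 / 0.208 = 2.14; SD of t = 0.764. P = Φ((2.14 - 1.67) / 0.764) = 0.73.

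**Step 4: simulated pass rates of the filled analysis, pooled maximum.**

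| Lost, placebo / Q-Urol | No effect | True 0.5 SD |
|---|---|---|
| 10% / 5% | about 8% | 92%* |
| 15% / 5% | 22% | 98%* |
| 5% / 5% | 2.6%* | 81% |
| 10% / 10% | 1.7% | 73% |
| 5% / 10% | 0.3% | 50% |

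*From the mean-20 run. Observed-case analysis gives about 5% and 87-88% throughout.

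**Step 5: does it flag a false positive?** With observed cases standing in for multiple imputation and no effect, both analyses pass in 4.9% of trials at 10%/5% and 5.1% at 15%/5%. The observed-case rate is itself about 5%, so essentially every false positive also passes the check.

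**Step 6: within-arm maximum.** At 15%/5% with no effect the pass rate is still 23%. At 10%/10% with a true 0.5 SD it is 81%, and the difference is not attenuated.

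**The case against.** The strongest reply is that this run decides nothing. Efficacy is judged on the multiple-imputation t statistic. A reader might infer from the 22% that the trial's Type I error is inflated, or that the rule creates a Q-Urol benefit. The documents do not support that: the run can only fail to flag a false positive. This stands.

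A reader might also infer that the rule is simply anti-conservative. That is wrong too. With equal losses, or more Q-Urol losses, it is stricter than the nominal level, and passing it then is real support. The plan calls the value worst; it never calls the analysis conservative.

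Third, the unfavourable cases assume more placebo loss in a double-blind trial with a matching placebo. If each patient is lost at random with one probability shared by both arms, the pass rate under no effect stays near nominal: 4.6%, 4.9% and 4.7% at 5%, 10% and 15%. This stands as a limit, since the documents give no reason to expect a placebo excess. But if the loss probabilities do differ, letting the counts vary makes matters worse: about 15% at 10%/5% and 34% at 15%/5%.

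Fourth, any stress test costs power. A 1 SD Q-Urol-only penalty at 10%/10% leaves 72%, close to the planned rule's 73%. That is fair, and to say the rule hides a real effect would be too strong at low equal loss.

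Fifth, the worst-score rule may be a numerical form of the treatment-failure rule in Section 12.3.2. That is plausible and a reason to keep it, but the plan does not say so.

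Finally, the lack of intermediate NIH-CPSI scores does not leave imputation without post-baseline information: the 28-day pain diary and weekly calls exist.

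**Conclusion.** The concern holds in a limited form. The one planned sensitivity analysis has no fixed direction. Under no effect its pass rate ranges from about 0.3% to 22% across the assumed loss patterns. Under a true 0.5 SD effect with equal or greater Q-Urol loss it ranges from 50% to 81%. Neither agreement nor disagreement with multiple imputation can be read without the missing counts by arm.

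The mechanism is algebraic and holds for the pooled and the within-arm maximum. The sizes rest on assumed dropout, mean and SD, and on losses completely at random in fixed numbers. The trial's own error rates are not shown to be affected. A reader might take the maximum to mean the patient's own largest score, which for a non-completer would be baseline. The wording does not suggest this, but one clause would exclude it. This is a worthwhile, inexpensive improvement rather than a flaw in the primary analysis.

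**What to change.** In Section 13.2.2, make the main sensitivity analysis a delta-adjusted (tipping-point) multiple imputation. Keep the planned imputation, add 0, 1, 2, ... NIH-CPSI points to imputed Q-Urol values only, and leave placebo imputations unpenalised. Report the penalty at which the pooled t statistic falls below the final critical value. This moves in one known direction. In an approximate check with penalties of 0, 0.25, 0.5 and 1 SD (0, 2, 4 and 8 points if the SD is 8), the pass rate under no effect at 15%/5% loss is 4.7%, 4.2%, 3.3% and 2.5%. At 10%/10% with a true 0.5 SD it is 87%, 84%, 80% and 72%.

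The worst-observed-value run may stay as a secondary analysis if the text:

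- says whether the maximum is pooled or within arm;
- reports missing counts by arm beside the result;
- reconciles it with the treatment-failure rule in Section 12.3.2.

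The cost is a short SAP edit, best made before unblinding, and a little more programming, with no new patients, visits or data. The downside is a stricter check that may make a positive primary result look less robust.

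### The 95% confidence interval planned for the primary endpoint does not match the one-sided 5% group-sequential test, and nothing adjusts it for the interim look

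*Combined protocol and SAP*

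**What the plan says.** **Decision rule (13.2.1).** The test statistic is the control mean minus the treatment mean of the peak NIH-CPSI total score, as a two-sample t. "A single interim analysis is planned after N1= 21 subjects per group have outcome data". At that look the trial stops for efficacy if t is "greater than 2.85 at the interim analysis the trial will be terminated for efficacy". The futility rule is: "If the t statistic has a value less than -1.16 at the interim analysis the trial will be terminated for futility". Otherwise it continues to 70 per group, where "the treatment will be deemed efficacious at the final analysis if the t statistic has a nominal value greater than 1.67". The design is sized for 90% power at "overall one-sided Type I error equal to 0.05", "to detect a 0.5 standard deviation lower mean of the primary endpoint in the treatment group compared to the control group".

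**Reporting (13.2.2, repeated in the Study Summary under Statistical Methodology).** Beside the formal test, "the mean change between groups and the mean change within each group together will be reported together with 95% confidence intervals". Neither place says whether the intervals are one- or two-sided, how they are computed, or whether they allow for the interim look.

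**Adjustment for the look.** The only one is in 13.2.1. It protects the Type I error of the final test if either analysis is run at an unplanned sample size. It does not concern the estimate or the interval.

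**Variable.** Section 12.2 determines efficacy by the mean difference between arms in the outcome variable, which is the tested contrast. Section 13.2.2 speaks of mean change.

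**The concern.** The result will be read as a decision plus an estimate with its interval, and the two should agree. Here the test spends 5% in one tail over two looks. A conventional 95% interval puts 2.5% in each tail and ignores the first look. Two things can follow.

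- The trial can declare efficacy while its published interval includes no effect. This is most likely where the evidence is weakest.
- A trial that stops at 42 patients reports only a difference large enough to cross a high boundary. The unadjusted estimate is then selected to be large, and its interval misses the truth more often than its label says.

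If the interval is chosen only after the result is known, the choice is open to criticism in either direction.

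**Working it through.** **Inputs.** All design inputs come from 13.2.1 and 13.2.2: 21 then 70 per group; bounds −1.16 and 2.85 at the interim and 1.67 at the end; effect 0.5 SD. Data are taken as normal with SD 1 and no missing values, using the pooled two-sample t (40 then 138 degrees of freedom). Results come from 1,000,000 simulated trials per scenario.

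**1. The plan's own figures.**

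| Quantity | Plan | Recomputed |
|---|---|---|
| Overall one-sided Type I error | 0.05 | 0.050 |
| Power at 0.5 SD | 90% | 90.1% |
| Early futility, null | 12% | 12.7% (12.3% with a z approximation) |
| Early futility, 0.5 SD | 0.3% | 0.3% |
| Early efficacy, 0.5 SD | 12% | 12.4% |

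The test is sound.

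**2. Level.** A two-sided 95% interval at the final look excludes zero only if t > t(0.975; 138) = 1.977. The success bound is 1.67. At t = 1.67:

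- estimate = 1.67 × √(2/70) = 0.282 SD
- half-width = 1.977 × √(2/70) = 0.334 SD
- 95% interval = −0.05 to 0.62 SD, with efficacy declared.

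The one-sided p at 1.67 is 0.0486, so the unadjusted interval that agrees with the bound has level 1 − 2 × 0.0486 = 90.3%.

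| True effect (SD) | Win with 95% interval covering zero, % of trials | % of wins |
|---|---|---|
| 0 | 2.3 | 46 |
| 0.25 | 11.1 | 26 |
| 0.4 | 10.3 | 14 |
| 0.5 | 6.3 | 7 |

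This arises only at the final look. An early stop at t > 2.85 always gives an unadjusted 95% interval for the tested difference that excludes zero.

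**3. Stopping rule.** An early efficacy stop needs an observed difference of at least 2.85 × √(2/21) = 0.88 observed SD, whatever the truth.

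| True effect (SD) | Early efficacy stop, % | Mean estimate given stop (SD) | Ratio to truth | Naive 95% coverage given stop, % |
|---|---|---|---|---|
| 0.4 | 7.2 | 0.96 | 2.40 | 65 |
| 0.5 | 12.4 | 0.99 | 1.97 | 80 |
| 0.6 | 19.9 | 1.01 | 1.69 | 88 |

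The 80% can be checked by hand. At 0.5 SD the interval's lower limit lies above the truth in 2.5% of all trials, and all of these are early stops: 2.5/12.4 ≈ 20% missed.

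**4. All trials at 0.5 SD.** The mean naive estimate is 0.5405, and 0.5405/0.5 = 1.08, so the bias is +8%. Naive 95% coverage is 93.7%.

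**5. Would relabelling to 90% be enough?** No. The naive 90% interval covers 87.3% at 0.5 SD. The 90% stagewise-ordering interval (normal approximation) at final t = 1.67 is 0.003 to 0.56 SD, so it excludes zero, to rounding, just as the test succeeds. At t = 1.977 it is 0.05 to 0.61 SD.

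**The case against.** **The interval only supplements the decision.** This stands. Section 13.2.2 offers the intervals in addition to formal testing, and they cannot change who wins. A reader might infer that the Type I error or the success criterion is faulty. Step 1 of the working shows that neither is.

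**A 95% interval beside a one-sided 5% test is a cautious habit.** Partly right. The 46% figure under the null means that the wider interval flags many false wins. That is a reason to keep it as labelled descriptive output. It is not a reason to leave the test without an interval that agrees with it.

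**Two-sidedness and a fixed-sample method are inferred.** This also stands. They are the ordinary reading of an unqualified 95% interval, but they are not stated. A one-sided 95% bound uses t = 1.656 at the final look and would exclude zero whenever t > 1.67. If that is intended, one phrase settles the level; the early-stop problem remains.

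**The variables may not differ.** A reader might infer that one variable is tested and another reported. The documents do not establish this. Section 12.2 names the difference in the outcome variable, and mean change between groups may be loose wording for it. On the other side, 13.2.3 uses change for pre-to-post differences, and a mean change within an arm can hardly be anything else. It is an ambiguity to reconcile. Any figure for its effect would depend on a baseline correlation and baseline SD that the documents do not give, so none is offered here.

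**The trial will not usually report twice the true effect.** Correct. That reading fits only early efficacy stops, about 12% of trials at 0.5 SD.

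**Conclusion.** The concern holds as a defect of estimation and reporting. Followed as written, 13.2.2 yields an interval that can contradict the 13.2.1 decision: 6.3% of trials and 7% of wins at the design effect, 26% of wins at 0.25 SD, 46% of false positives. It also yields an uncorrected estimate after an early efficacy stop, averaging about 0.99 SD against a true 0.5 SD, with about 80% coverage. Over all trials the harm is modest.

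These sizes assume normal data, complete outcomes, the planned sample sizes, a two-sided 95% interval for the tested difference, and no adjustment for the look. They do not support the claim that the decision rule is invalid, that effects are generally doubled, or that the reported variable is proven to differ from the tested one. The text should be changed before unblinding.

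**What to change.** In 13.2.2, and in the matching Study Summary text:

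1. State that the between-arm difference in the tested NIH-CPSI variable (12.2) is the reported primary estimate. Reconcile the mean-change wording with it.
2. Give that difference an interval that accounts for the interim look and matches the one-sided 5% test: for example a two-sided 90% stagewise-ordering interval, or the equivalent one-sided 95% bound.
3. Keep the conventional 95% interval and the within-arm mean changes if wanted, labelled descriptive.
4. After an early efficacy stop, report a bias-adjusted estimate next to the naive one and say that the naive one is inflated by selection.

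Item 2 does not replace item 4. For a stop at the first look, stagewise ordering gives the same limits as the fixed-sample 90% interval. It restores agreement with the test and coverage over all trials, but not coverage among early stops. By the reasoning in step 3 of the working, at 0.5 SD about 5/12.4 ≈ 40% of early-stop 90% intervals would miss the truth. The report should say so.

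**Cost.** A few sentences and minor programming, including a rule for combining the adjusted interval with the multiple imputation in 13.2.2, and a less favourable estimate after an early stop. Sample size, boundaries, visits and power do not change. Keeping the two-sided 95% interval as the primary one and raising the final bound to about 1.977 would also remove the final-look contradiction. However, it cuts overall alpha to 0.027 and power to 83.8%, and leaves the early-stop bias in place.

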13.2.3 Secondary endpoint

- 1. Patient questionnaires administered pre- and post-study therapy: The Expanded Prostate Cancer Index Composite (EPIC), The International Prostate Symptom Score (I-PSS), The Rectal Function Assessment Score (R-FAS), and the Sexual Health Inventory for Men (SHIM). The change in questionnaire scores will be compared between groups using two-sample *t*-tests. If normality assumptions are violated, non-parametric Wilcoxon tests may be used. Confidence intervals for the mean change between and within groups will also be reported.
- 2. Inflammation markers pre and post brachytherapy: erythrocyte sedimentation rate, C-reactive protein, and prostate-specific antigen (PSA). The change in inflammatory markers will be compared between groups using two-sample t-tests. If normality assumptions are violated, non-parametric Wilcoxon tests may be used. Confidence intervals for the mean change between and within groups will also be reported. For laboratory markers that are known to be positivity skewed, such as CRP, the analyses will be based on the log-transformed values.
- 3. The frequency of adverse events (AEs) will be collected and characterized by type, severity (as defined by CTCAE, version 5.0), seriousness, duration, and relationship to study treatment. Counts and proportions of patients with adverse events will be tabulated and exact 95% binomial confidence intervals will be reported.
- 4. The number of days during the 28 days post-brachytherapy that any medication is taken for the treatment of prostate-related pain will be summarized using the mean, median and interquartile range. A Wilcoxon test will be used to compare the arms.

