1.2 Secondary Objective(s)

1.2.1 To assess Health-Related Quality of Life (HRQOL) in the urologic, rectal, sexual, hormonal, mental and overall physical domains of men receiving either placebo or supplement after definitive brachytherapy.

Secondary Endpoint: Patient questionnaires administered pre- and post-study therapy: The Expanded Prostate Cancer Index Composite (EPIC), The International Prostate Symptom Score (I-PSS), The Rectal Function Assessment Score (R-FAS), and the Sexual Health Inventory for Men (SHIM).

1.2.2 To assess if the Q-Urol has any significant impact on serum biomarkers of inflammation relative to placebo.

Secondary Endpoint: Inflammation markers pre and post brachytherapy: erythrocyte sedimentation rate, C-reactive protein, and prostate-specific antigen (PSA)

1.2.3 To access if the addition of Q-Urol introduces any additional toxicity relative to placebo.

Secondary Endpoint: Frequency of adverse events (AEs) will be collected and characterized by type, severity (as defined by CTCAE, version 5.0), seriousness, duration, and relationship to study treatment.

1.2.4 To assess the effect on prostatitis-related pain in men with localized prostate cancer following brachytherapy taking Q-Urol relative to placebo.

Secondary Endpoint: The number of days during the 28 days post-brachytherapy that any medication is taken for the treatment of prostate-related pain.

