4 STUDY DESIGN

4.1 Description

This is a Phase 2, double-blinded, placebo-controlled trial assessing the safety of Q-Urol use after brachytherapy placement in patients with localized prostate cancer. Patients will be randomized in a 1:1 ratio to receive Q-Urol/Placebo twice daily for six weeks after brachytherapy placement. Questionnaires will be administered pre- and post-treatment to assess the change in prostatitis symptoms and quality of life measures. The mean values between groups will be compared.

Once 42 patients (21 to each arm) have been enrolled and treated on the study therapy, enrollment will be placed on hold and an interim analysis conducted. The interim analysis will be conducted for futility and efficacy and will be reviewed by the DSMC. If the analysis is favorable, as defined in the Statistical Analysis section, the trial will open to the enrollment of 98 additional subjects, 49 per arm. However, if the analysis does not demonstrate standards defined in the statistical analysis, the trial will be closed to accrual.

Version Date: 11APR2023

Safety monitoring will be overseen by the DSMC at HCI. See Section 12.4 for safety monitoring plan and early stopping rules.

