4.3 Number of Patients

The trial will enroll up to 70 patients to each arm, 140 patients total.

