12.3 Population for analyses

12.3.1 Evaluable for toxicity

Subjects who have received one dose of Q-Urol will be evaluable for toxicity.

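### The toxicity objective asks for a comparison with placebo, but the adverse event analysis plans no between-arm estimate

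*Combined protocol and SAP*

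**What the plan says.** Objective 1.2.3 is comparative: "To access if the addition of Q-Urol introduces any additional toxicity relative to placebo". The endpoint beneath it is the frequency of adverse events, described by type, CTCAE grade, seriousness, duration and attribution.

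Section 13.2.3 item 3 supplies the analysis: "Counts and proportions of patients with adverse events will be tabulated and exact 95% binomial confidence intervals will be reported". It names no risk difference, ratio, test or interval for a contrast, and does not say that the tables are split by arm.

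The other items in 13.2.3 each name a comparison:

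- Item 1: "The change in questionnaire scores will be compared between groups".
- Item 2: "The change in inflammatory markers will be compared between groups using two-sample t-tests".
- Item 4: "A Wilcoxon test will be used to compare the arms".

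The toxicity population in section 12.3.1 is: "Subjects who have received one dose of Q-Urol will be evaluable for toxicity". Placebo recipients are not mentioned. Allocation is 1:1 (section 4.1), with up to 70 patients per arm (section 4.3).

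**The concern.** The objective and its analysis do not match. Brachytherapy itself causes symptoms in almost every patient (section 2.1), so an adverse event proportion on Q-Urol alone cannot separate the supplement from the procedure. Only the contrast with placebo can. The rationale in section 2.2 is benefit over placebo at no cost in toxicity. The second half of that claim needs an estimate of the difference and a statement of its precision, and the plan provides neither. The wording of 12.3.1 adds to the problem: taken literally, it leaves the comparison without a comparator group.

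**Working it through.** **1. Does another section supply the contrast?**

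| Section | Content | Adverse events compared between arms? |
|---|---|---|
| 12.1 | Descriptive safety evaluation | No |
| 12.4 and Table 3 | Stopping rule for drug-related grade ≥3 SAEs, with fixed rates of 5% (acceptable) and 15% (excessive) | No |
| 13.2.3 item 3 | Counts, proportions, exact binomial intervals | No |
| 13.2.4 | ANCOVA for score changes | No |

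**2. The plan's own toxicity figures.** Table 3 is the only numerical toxicity design. The check was an exact binomial recursion over looks at 10, 21, 30, 40, 50, 60 and 70 patients, stopping when the count exceeds 2, 3, 3, 4, 5, 6 and 6. At a true rate of 5% it gives a crossing probability of 10.9%, early stopping of 9.1% and an average sample size of 66.4. At 15% it gives 93.4%, 87.6% and 32.6. All six rows of Table 3 agree. The table is therefore correct, and it follows a one-sample model against fixed rates with no placebo reference.

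**3. What separate intervals leave out.** The counts below are assumed. The 70 per arm comes from section 4.3.

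Inputs: Q-Urol p₁ = 15/70 = 21.4%; placebo p₂ = 5/70 = 7.1%.

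- Exact (Clopper–Pearson) 95% intervals: 12.5–32.9% and 2.4–15.9%. They overlap between 12.5% and 15.9%.
- Risk difference: d = 21.4 − 7.1 = 14.3 points.
- Newcombe interval, built from the Wilson limits (l, u) of each arm: lower = d − √[(p₁ − l₁)² + (u₂ − p₂)²]; upper = d + √[(u₁ − p₁)² + (p₂ − l₂)²].
- Wilson limits: 13.4–32.4% and 3.1–15.7%.
- Lower: 14.3 − √(8.0² + 8.5²) = 14.3 − 11.7 = 2.6. Upper: 14.3 + √(11.0² + 4.1²) = 14.3 + 11.7 = 26.0.

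The interval for the difference excludes zero (Fisher p = 0.028), which the two separate intervals do not show.

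A second assumed case, 26/70 against 14/70, behaves the same way. The exact intervals are 25.9–49.5% and 11.4–31.3%; the difference is 17.1 points (95% CI 2.2 to 31.2; Fisher p = 0.039).

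**4. How often would this happen?** Overlapping exact intervals together with Fisher p < 0.05 occur in a limited band. With 7 placebo events out of 70 the band is 17 to 20 Q-Urol events; with 14 it is 26 to 30. Above the band, the separate intervals no longer overlap.

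**5. What can 70 per arm resolve?** Power of a two-sided 0.05 comparison, all rates assumed:

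| Placebo v Q-Urol | z-test | Fisher exact |
|---|---|---|
| 5% v 15% | 0.51 | 0.41 |
| 10% v 25% | 0.65 | 0.58 |
| 20% v 40% | 0.74 | 0.68 |
| 30% v 50% | 0.68 | 0.61 |

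For 5% v 15%, 80% power would need 141 per arm (160 with continuity correction). If the trial stops at 21 per arm, power for that contrast is 0.19 (z-test) or 0.08 (Fisher).

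**The case against.** The strongest reply is that item 3 analyses the endpoint as written, namely the frequency of adverse events, and that descriptive tables are a defensible choice for an unpowered secondary safety endpoint in phase II. In a 1:1 randomised trial, by-arm tables are the natural reading, and any reader with by-arm counts can derive the risk difference. Serious harm is also watched by the stopping rule in 12.4 and by a monitoring committee that knows the allocation (4.2) and reviews all SAEs monthly (16.3). The wording of 12.3.1 is probably shorthand, since the efficacy population in 12.3.2 is worded the same way.

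Much of this stands. It rules out a formal test as the remedy and keeps the point small. It does not supply the missing estimate: the plan leaves the contrast to the reader, the by-arm split is not stated, and the monitoring arrangements do not specify a placebo contrast.

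A reader might go further and infer that the plan would hide a clear excess of adverse events, or lead to a false finding of no added toxicity. The documents do not support that. They set no rule based on interval overlap, and no margin or decision rule for declaring toxicity equal. The overlap band in step 4 is narrow, and larger excesses do separate the intervals. A risk difference whose interval includes zero could be misread in the same way, so the fix must carry a warning.

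**Conclusion.** The point holds as a gap between objective and analysis: a comparative toxicity objective has no between-arm estimate, while the other three secondary endpoints each have a comparison. The population definition in 12.3.1 needs the matching correction.

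The numerical size rests on assumed event counts and rates, because the documents give none. In the 15/70 v 5/70 illustration, the omitted quantity is a difference of 14.3 points with an interval of 2.6 to 26.0. At 70 per arm such intervals are wide, and power for the assumed differences of 10 to 20 points is about 0.4 to 0.75. That favours estimation over testing.

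No stated figure is wrong, Table 3 reproduces, and the primary inference is unaffected. This is a cheap improvement.

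**What to change.** In section 13.2.3 item 3:

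- State that adverse events are tabulated by arm, and keep the exact by-arm intervals.
- Add the Q-Urol-minus-placebo risk difference with a 95% CI (for example Newcombe) for patients with any adverse event, any grade ≥3 event, any SAE and any treatment-related event.
- Say which attribution categories count as related. Section 12.4 uses definite or probable, while the FDA reporting rules in 16.5.1 also include possible.
- Label these contrasts as estimation without a formal test, and state that an interval including zero does not show absence of added toxicity.

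In section 12.3.1, define the toxicity population as patients who received one dose of Q-Urol or placebo.

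The cost is a few sentences and one extra table, with no new data. The downside is that the intervals will be wide at 70 per arm, and wider still if the trial stops at the interim analysis with 21 per arm.
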